## ***Varenicline for the Treatment of DSM 5 Cannabis Use Disorder in Adults***

### **Study Overview and Design**

Although cannabis use is widespread and basic science research on cannabinoids is well-developed, advancements in medication development for cannabis use disorder (CUD) have been limited. Varenicline, a selective nicotinic nACh receptor partial agonist of the  $\alpha 4\beta 2$  subtype and a full agonist of the  $\alpha 7$  subtype, is arguably the most effective pharmacotherapy for promoting tobacco abstinence, and has also shown promise for the treatment of alcohol use disorder. Varenicline may improve cannabis use outcomes through multiple mechanisms, including interaction with the mesolimbic dopamine system, enhancement of cognitive functioning, and restoration of inhibitory control. To date, however, varenicline has not been evaluated in individuals specifically seeking treatment for CUD. Through the UG3/UH3 mechanism we proposed to rapidly yet thoroughly assess the utility of varenicline for CUD to potentially advance varenicline through the FDA's drug development approval pipeline. In the UG3 component, we conducted a six-week, placebo-controlled proof-of-concept clinical trial of varenicline for CUD, paired with pre- and post-evaluations of cognitive functioning and neural circuitry involved in cannabis cue reactivity and inhibitory control to elucidate the pharmacodynamics of varenicline as a treatment for CUD. We successfully met the pre-specified Go/No Go criteria for the UG3 study. For the the UH3 component, we will extend our promising UG3 findings by conducting a 12-week, placebo-controlled, double-blind trial to determine the impact of varenicline on cannabis use outcomes.

**Specific Aim 1.** To evaluate the efficacy of varenicline for cannabis use disorder (CUD). **Hypothesis 1:** A 12-week treatment course of varenicline, compared to placebo, for CUD will yield significant reduction in cannabis use.

**Specific Aim 2.** To examine the safety and tolerability of varenicline, compared with placebo, when used for CUD. **Hypothesis 2:** A 12-week treatment course of varenicline, compared to placebo, will demonstrate adequate safety and tolerability, as defined by non-inferiority in the frequency of treatment-emergent adverse events.

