### **Statistical Analysis**

**Data Management Plan.** All data will be entered into a standard software package (REDCap). Macro programs will be written to check the data for logical consistency and values out of possible range. Quarterly database management and data integrity audits will be conducted.

**Baseline Analysis.** Categorical clinical and demographic variables will be assessed for balance between groups with chi-square tests of independence, while continuous variables will be assessed using Student's *t*-test. In addition to baseline group differences, preliminary analysis of baseline characteristics with cannabis use outcomes of interest will examine significant correlates of use reduction and abstinence. Characteristics found to be significantly associated with cannabis use outcomes will be included as covariates in the initial stages of adjusted statistical model development.

**Primary Analysis.** The primary aims for the UH3 portion of the protocol are to test the efficacy and safety of varenicline for CUD during a 12-week placebo-controlled trial. **Specific Aim 1:** The primary efficacy outcome is cannabis use reduction as measured by daily substance use logs and examined as the total number of use sessions at each weekly visit (primary interest weeks 6-12). Group differences in reported session use will be examined utilizing a generalized mixed effects models using a log-linear framework for count data. A Poisson distribution will be assumed with a logarithm link function will be used to assess the effects of varenicline treatment, time, and the appropriate interaction. Overdispersion in discrete count models can have a significant

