impact on parameter inference, thus when detected, a negative binomial distribution will be specified and model fit will be compared to the Poisson model. An offset variable will be included in the models to account for possible differences in between visit timing. Models will be computed both adjusted for design variables and for significant covariates and confounders found in the preliminary analysis. Working correlation structures will be independently compared using the quasi-likelihood under the independence model criterion statistic (QIC). Model based means will be used to construct the pairwise comparisons between groups. All design adjusted models will include baseline average use sessions, study visit, treatment group assignment and randomization stratification variables (smoking status and gender). Additional exploratory approaches (e.g., analysis excluding participants with <80% medication adherence, per protocol analysis, completers analysis) will be undertaken.

**Specific Aim 2:** We will also compare the frequency of treatment-emergent AEs between treatment groups using a non-inferiority analysis. Of particular interest will be AEs leading to medication discontinuation and the occurrence of treatment-related serious AEs (SAEs). We will specifically compare neuropsychiatric AEs and suicidality (C-SSRS) ratings by treatment group. We hypothesize that treatment with varenicline will not cause undue adverse events and will be non-inferior to the placebo group by a margin ( $\delta$ ) of no more than a 10% using the Farrington-Manning score test for non-inferiority.

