substance use report logs. We anticipate the increased information will allow better precision in the estimated effect between randomized study groups. Assuming this, coupled with the more extended 12-week treatment compared with the truncated treatment phase in the prior UG3 proof-of-concept trial, results in a slightly increased effect size of  $d=0.5$ , a high correlation between measures taken over time on the same participant ( $p=0.95$ ) and a 5% type 1 error rate, 57 participants are necessary in each treatment arm to achieve adequate power (80%). Additionally, the UG3 noted a higher than expected attrition rate of 35%, thus we anticipate that, despite our best efforts and revised approach, attrition during the study could reach 35%. Thus to ensure that we have the appropriate sample, we will enroll and randomize **approximately 90 participants per group for a total sample size of approximately n=180**. This will allow us to detect a difference in cannabis use session of at *least*  $d=0.5$  between randomized study groups while accounting for up to 35% study attrition. Similar to adult varenicline phase III studies (Gonzales et al., 2006), for the primary safety analysis we will compare the frequency of all treatment-emergent AEs (defined as any AE occurring between treatment initiation and one week following treatment conclusion), SAE's between varenicline and placebo groups. A non-inferiority analysis will be utilized (Piaggio et al., 2006). With an estimated placebo treatment-emergent AE rate of 75% (Gonzales et al., 2006), 90% power and two sided  $\alpha = 0.05$ , within our proposed sample of **approximately 180 randomized participants** we will be able to detect a 10% non-inferiority margin in AE frequency between treatment groups if it exists.

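### The 90% power stated for the primary safety non-inferiority test is not supported: no varenicline AE rate is given, and equal 75% rates at 90 per arm give about 34% (46% at one-sided 0.05)

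*Combined protocol and SAP*

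**What the plan says.** The Primary Analysis paragraph puts safety alongside efficacy: "The primary aims for the UH3 portion of the protocol are to test the efficacy and safety of varenicline for CUD". Hypothesis 2, in Study Overview and Design, describes adequate safety and tolerability "as defined by non-inferiority in the frequency of treatment-emergent adverse events". The Specific Aim 2 paragraph of Statistical Analysis names the test and margin: varenicline is to be non-inferior by "no more than a 10% using the Farrington-Manning score test for non-inferiority".

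The Power and Sample Size paragraph gives the inputs to the safety power claim:
- "With an estimated placebo treatment-emergent AE rate of 75" per cent, taken from a cited phase III smoking-cessation trial
- "90% power and two sided" alpha of 0.05
- the sample already fixed for efficacy, "approximately 90 participants per group for a total sample size of approximately n=180"

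It concludes that "we will be able to detect a 10% non-inferiority margin in AE frequency between treatment groups if it exists". Neither paragraph gives an expected AE rate on varenicline. The nearest statement is the hypothesis that "treatment with varenicline will not cause undue adverse events and will be non-inferior to the placebo group" within the margin.

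**The concern.** The power of a non-inferiority test depends on the true rate in both arms, and the plan gives only one of them. Under the usual planning assumption of equal rates, a 10-point margin on a 75% event rate needs several hundred participants per arm, so 90% power from 90 per arm looks far too high.

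The figure matters because Hypothesis 2 rests on this one test. A reader who trusts 90% power could take a failed test as evidence that varenicline is harmful, when failure is the expected result of low power even if the drug adds no AEs at all.

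Two limits apply. The same section says the study is powered on the efficacy hypothesis, so the error is in the safety power claim and not in how the sample size was chosen. The other safety comparisons under Specific Aim 2 (discontinuations, serious AEs, neuropsychiatric AEs, C-SSRS) do not depend on this figure.

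**Working it through.** **Inputs from the documents.** Placebo AE rate pP = 0.75; margin 0.10, read as an absolute difference; n = 90 per arm; two-sided alpha 0.05, which is one-sided 0.025 for a non-inferiority test; Farrington-Manning score test. One-sided 0.05 is shown as well, in case that was meant.

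**Input not in the documents.** The varenicline rate pV. The base case is pV = 0.75 (our assumption), with a range below.

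**Step 1: try to reproduce 90% (normal approximation).**
Power = Φ[(0.10 − (pV − pP))/SE − z], with SE = √[pV(1−pV)/n + pP(1−pP)/n].
- SE = √(2 × 0.1875/90) = 0.0645, and 0.10/0.0645 = 1.549.
- One-sided 0.025: Φ(1.549 − 1.960) = 34.1%.
- One-sided 0.05: Φ(1.549 − 1.645) = 46.2%.

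The stated 90% does not reproduce.

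**Step 2: exact power of the named test.** The statistic is (observed difference − 0.10) divided by its standard error, with the two rates estimated under the constraint that they differ by 0.10. Evaluating it in all 91 × 91 = 8,281 possible outcome tables and summing the binomial probabilities of those that pass gives, with placebo at 75% and 90 per arm:

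| True varenicline rate | Power, one-sided 0.025 | Power, one-sided 0.05 |
|---|---|---|
| 65% | 83.8% | 90.2% |
| 70% | 62.0% | 73.2% |
| 75% | 34.0% | 46.5% |
| 80% | 12.2% | 20.0% |
| 85% (margin boundary) | 2.5% | 5.0% |

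The last row is a size check, and it returns the nominal alpha. If both arms share a rate of 70% or 80% instead, power at one-sided 0.025 is 31% or 38%.

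**Step 3: what would give 90%.**
- Sample size at equal 75% rates: (1.960 + 1.282)² × 0.375/0.10² gives 395 per arm (one-sided 0.025); (1.645 + 1.282)² × 0.375/0.10² gives 322 per arm (one-sided 0.05). Exact power at both sizes is 90.1%.
- Varenicline rate at 90 per arm: about 63% (one-sided 0.025) or 65% (one-sided 0.05), that is, 12 or 10 points below placebo.
- Margin at 90 per arm and equal rates: about 21 or 19 points.

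**Step 4: other readings.** All use equal 75% rates, with results at one-sided 0.025 and 0.05.
- Taking 180 as the size of each arm: 59% and 71%.
- Taking the margin as 10% of 75%, or 7.5 points: 21% and 31%.
- Applying a continuity correction: 28% and 39%.

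None gives 90%.

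**Step 5: what a pass requires.** Suppose 68 of 90 placebo participants have an AE (75.6%). At one-sided 0.025:
- 65 of 90 on varenicline (72.2%) passes: z = −2.03, upper limit of the 95% score interval 9.5 points.
- 66 of 90 fails: z = −1.87, upper limit 10.6 points.
- Identical counts, 68 against 68, give an interval of −12.6 to +12.6 points and fail.

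Varenicline must therefore be observed about 3.3 points below placebo (3/90) to be declared non-inferior.

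**Step 6: how trials would end.** Share of trials at one-sided 0.025, placebo 75%, with the 95% score interval that inverts the test:

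| True varenicline rate | Pass | Fail, interval includes 0 and 10 points | Interval wholly above 0 |
|---|---|---|---|
| 75% | 34.0% | 63.5% | 2.5% |
| 80% | 12.2% | 75.7% | 12.1% |
| 85% | 2.5% | 58.9% | 38.6% |
| 90% | 0.2% | 23.1% | 76.7% |

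**The case against.** The best defence is that the varenicline rate is a free input, so the claim is incomplete and not demonstrably miscalculated. One combination does return the figure: a 65% varenicline rate at one-sided 0.05 gives 90.2%. It is true that 34% rests on an assumed varenicline rate. But that combination departs from the stated two-sided 0.05, at which it gives 84%, and it supposes 10 points fewer AEs on the active drug. No section assumes that. Potential Risks cites relative risks above 1 for nausea (3.21), insomnia (1.50), abnormal dreams (2.79) and headache (1.20). Those concern individual events and show direction only, but the direction is against the assumption needed. Any varenicline rate at or above placebo gives at most 34% (46%).

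Three smaller points have some force. The plan writes 10% without saying absolute; that is the natural reading, and the relative reading makes power worse. Because the cited relative risks exceed 1, equal rates may themselves be optimistic, so 34% should not be taken as a conservative figure. Finally, an inconclusive label would also cover 58.9% of trials in which varenicline truly has a 10-point excess, so it must not be read as reassurance.

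**Conclusion.** The concern holds. The plan states 90% power for the test that defines Hypothesis 2, and at 90 per arm the design has about 34% (one-sided 0.025) or 46% (one-sided 0.05) if both arms have a 75% AE rate. In that case the trial fails its own safety definition 66% of the time (54% at one-sided 0.05).

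The exact figure depends on the assumed varenicline rate, an absolute 10-point margin and all 90 per arm being counted. The conclusion does not depend on equal rates in particular: 90% is out of reach unless varenicline truly causes about 10 to 12 points fewer AEs than placebo. The claim must be corrected.

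**What to change.** In Power and Sample Size, delete the 90% claim. State the assumed varenicline AE rate with a reason, the one-sided alpha, that the margin is 10 percentage points, and the power that follows: about 34% at equal 75% rates and one-sided 0.025. Showing power over a range of varenicline rates would be better than a single figure.

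In Specific Aim 2, keep the Farrington-Manning test, the margin and Hypothesis 2's definition, with non-inferiority read from that test alone. Add the AE risk difference with the 95% score interval that inverts the test. An upper limit below 10 points agreed with the test in all 8,281 outcome tables at 90 per arm, so the two cannot disagree. Prespecify that a failed test whose interval includes both 0 and 10 points is inconclusive: it does not show non-inferiority and is not in itself evidence of harm. An interval wholly above zero falls outside that rule and should be reported as an AE excess.

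The cost is a few sentences; the sample size, test, margin and success definition do not change. The drawback is candour: the plan would disclose that an inconclusive result is the most likely one at equal 75% rates (about 63%), and that the inconclusive category would also take in many trials with a real excess.

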## **PROTECTION OF HUMAN SUBJECTS**

### **RISKS TO THE SUBJECTS**

#### *a. Human Subjects Involvement and Characteristics*

Admission into the study is open to men and women and to all racial and ethnic groups, age 18 and over. Approximately one hundred and eighty individuals (across two participating sites) with cannabis use disorder will be recruited primarily through clinical referrals and internet and newspaper advertisements. Inclusion/exclusion criteria that apply to all participants are listed below:

#### **Inclusion Criteria**

- Must meet DSM-5 criteria for cannabis use disorder and use cannabis at least 3 days per week in the last 30 days.
- Express interest in receiving treatment for cannabis use disorder and reducing use.
- Must be at least 18 years of age.
- If female and of childbearing potential, must agree to use acceptable methods of birth control for the duration of the trial.

- Must consent to random assignment, and be willing to commit to medication ingestion.
- Must be able to read and provide informed consent.
- Must have body weight >110lbs (50kg) and have BMI between 18 and 35kg/m^2
- Must function at an intellectual level and have knowledge of the English language to sufficiently allow for accurate completion of assessments..

### **Exclusion Criteria**

- Women who are pregnant, nursing, or plan to become pregnant during the course of the study.
- Individuals with severe renal impairment (creatinine clearance less than 30 mL per minute).
- Lifetime history of DSM-5 Bipolar I or II Disorder, Schizophrenia or other psychotic disorder. Stably treated MDD, Dysthymia, GAD, Social Phobia, and Specific Phobia diagnoses are acceptable (i.e. same dose of medication has been prescribed for at least 2 months prior to screening and no changes in current medication expected during course of the trial).
- Past year or current posttraumatic stress disorder.
- Subjects who are actively suicidal, or who report suicidal ideation (SI) with intent or plan in the past year.
- Past year or current posttraumatic stress disorder.
- Subjects who are actively suicidal, or who report suicidal ideation (SI) with intent or plan in the past year.
- Subjects who have a SBQ-R total score  $\geq 8$ , or for whom the investigator judges that a risk assessment by a qualified medical professional is required. Subjects answering 'yes' on questions 4 or 5 of C-SSRS will be referred to assessment by a qualified mental health professional.
- Suicidal behavior within the past 10 years or a lifetime history of serious or recurrent suicidal behavior.
- Subjects who are believed to be at homicidal risk. Concomitant use of psychotropic medications, with the exception of stable doses (defined as no dosing adjustments in the past two months) of non-MAO-I antidepressants, non-benzodiazepine anxiolytics, and ADHD medications.
- Current use of medications prescribed for mania or psychosis.
- Current use of bupropion or nortriptyline.
- Moderate or severe non-cannabis substance use disorders within the past 60 days with the exception of tobacco use disorder.
- Past year or current moderate or severe alcohol use disorder.
- Individuals taking an investigational agent within the last 30 days before baseline visit.
- Individuals with clinically significant medical disorders or lab abnormalities.
- Any individual at screening with SGOT (AST) or SGPT (ALT) greater than 3 times the upper limit of normal and/or total bilirubin greater than two times the upper limit of normal.
- Individuals with clinically significant cardiovascular disease in the past 6 months (e.g., myocardial infarction, CABG, PTCA, severe or unstable angina, serious arrhythmia, or any clinically significant ECG conduction abnormality).
- Individuals with clinically significant cerebrovascular disease in the past 6 months such as TIA, CVA, or stroke.
- Hypersensitivity to varenicline.
- Individuals who have participated in the clinical trial of any investigative compound within the last 60 days.
- Individuals who are on probation or under a mandate to obtain treatment.
- Individuals with plans to initiate or change frequency of attendance at self-help meetings (e.g. AA, NA).

### ***b. Sources of Materials***

Research material obtained from individual participants includes questionnaires and in-person and remote interviews with study personnel, and blood and urine samples. To ensure confidentiality, all participant data will be letter/number coded, and only the investigators will have access to the master lists of codes. The research material will be obtained specifically for research purposes. Written research material obtained will be stored in the Addiction Sciences Division at MUSC or at Behavioral Health Services of Pickens County in Pickens, SC, in an office that is locked when not in use. Urine samples from MUSC site will be stored in the Clinical Neurobiology

Urine samples from the Pickens site will be stored at Behavioral Health Services of Pickens County and then sent to MUSC CNL for analysis in batches.

*c. Potential Risks*

The varenicline package insert details adverse events associated with the medication. Specifically, it reports that "the most common adverse reactions (>5% and twice the rate seen in placebo-treated patients) were nausea, abnormal (e.g., vivid, unusual, or strange) dreams, constipation, flatulence, and vomiting." Meta-analyses of the four main adverse events in varenicline versus placebo groups in adult trials yielded relative risks (RRs) of 3.21 (95% CI 2.71, 3.80) for nausea, 1.50 (95% CI 1.26, 1.79) for insomnia, 2.79 (95% CI 2.09, 3.72) for abnormal dreams, and 1.20 (95% CI 1.00, 1.45) for headache (Cahill et al., 2009). While post-marketing anecdotal reports of psychiatric adverse events led to an FDA "black box" warning for varenicline, a reanalysis of controlled trials revealed no evidence that varenicline is associated with neuropsychiatric adverse events (Thomas et al., 2015). There is a potential risk of loss of confidentiality.

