detection cut-off value of 30.00 ng/ml (Abbott AXSSYM® System package insert). Urine creatinine will also be obtained, as creatinine normalization has been proposed as a method to differentiate new cannabis use from residual drug excretion (Huestis and Cone, 1998; Schwilke et al, 2011). **Urine Cotinine:** Nicotine is metabolized to cotinine by the liver. Cotinine has a longer half-life than nicotine, and thus serves as a more reliable biomarker of cigarette smoking (Zevin et al., 2000). Urine will be screened qualitatively at each visit (detection cut-off value of 200 ng/ml). **Marijuana Craving Questionnaire (MCQ):** The MCQ (Heishman et al, 2001) is a Likert-based self-assessment of cannabis craving shown to be a valid and reliable instrument for measuring cannabis craving. The 12-item MCQ will be used, which has been constructed by selecting the three items from each factor of the full 47-item MCQ that exhibited the most within-factor reliability (Heishman et al, 2009). **Cannabis Withdrawal Scale:** The Cannabis Withdrawal Scale (Allsop et al, 2011) is comprised of 19 items for which participants rate severity of symptoms in the previous 24 hours. **Marijuana Use Summary Sheet/Self-Efficacy Questionnaire/Marijuana Problem Scale/Reasons for Quitting Questionnaire:** These worksheets, created by Stephens and colleagues (2000), will be used to gather information from participants to prepare personalized feedback reports (PFRs) for use in the motivational enhancement sessions. **DSM-5 Criteria for CUD:** DSM-5 criteria will be assessed at four time points to determine changes in severity of cannabis use disorder.

**Safety Assessment. Review of Adverse Events:** Adverse events (AEs) will be assessed weekly by study personnel. The type of AE, severity of AE, and the relationship to study medication will be recorded. AEs will be coded on a weekly basis using Medical Dictionary for Regulatory Activities (MedDRA) rules.

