**Exploratory Analysis.** **Exploratory Aim 1:** Negative affect will be measured weekly during study treatment and compared between groups using generalized linear mixed effects regression models. Model based means will be used to construct the pairwise comparisons between groups and treatment by time interactions will be included to assess differential response over time. **Exploratory Aim 2:** Further, we will assess the time varying relationship between changes in negative affect and cannabis use sessions. Cross lagged panel models will be used to assess the lagged effect of changes in negative affect on cannabis use and visa-versa. Models will also include the autoregressive and synchronous relationships between these variables over time. Models will evaluate the influence of study treatment and medication adherence on the relationship between negative affect and cannabis use through the inclusion of time variable and time invariate effects. If significant treatment effects exist, additional stratified analysis will be conducted to elucidate the magnitude and direction of the effect.

**Additional Data Analysis.** Logistic regression models will be used to assess end of study abstinence (7 day point prevalence abstinence at week 12 and continuous abstinence from week 6 to 12); primary analysis models will be reported both as design adjusted results as well as adjusted for significant clinical covariates. To comprehensively examine the longitudinal efficacy of varenicline, weekly cannabis abstinence will also be analyzed over the entire treatment course using generalized linear mixed effects regression models under a GEE framework. Between study visit cannabis use will be based on daily substance use diaries confirmed via Time-Line Follow-Back procedures. The number of treatment visits attended will be compared between groups using Poisson regression models, while the number of days retained will be assessed using Cox Proportional Hazards regression models. Medication adherence (REDCap video capture of medication-taking; pill counts), tobacco smoking status, and gender will be explored as potential moderators of study outcomes through model interactions. Craving and withdrawal from cannabis will be assessed between groups over time using generalized linear mixed effects models.

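### Cannabis withdrawal is compared between arms on a 19-item symptom-severity scale, with no step to separate withdrawal from symptoms that varenicline itself can cause

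*Combined protocol and SAP*

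**What the plan says.** All references are to the combined protocol and SAP.

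- **Statistical Analysis, Additional Data Analysis:** "Craving and withdrawal from cannabis will be assessed between groups over time using generalized linear mixed effects models". No item-level or sensitivity analysis is attached to this comparison.
- **Substance-Related Instruments, Cannabis Withdrawal Scale:** the scale "is comprised of 19 items for which participants rate severity of symptoms in the previous 24 hours". The items are not named, and the description does not say whether a rating is limited to symptoms with a particular cause.
- **Table 6, Schedule of assessments:** the scale has 14 marks, which fits baseline, weeks 1 to 12 and the follow-up visit. On that reading it is scored throughout dosing.
- **Risks to the Subjects, c. Potential Risks:** pooled adult trials of varenicline against placebo gave "relative risks (RRs) of 3.21 (95% CI 2.71, 3.80) for nausea, 1.50 (95% CI 1.26, 1.79) for insomnia", then "2.79 (95% CI 2.09, 3.72) for abnormal dreams, and 1.20 (95% CI 1.00, 1.45) for headache". The package insert, as cited there, also names constipation, flatulence and vomiting.
- **Safety Assessment, Review of Adverse Events:** "The type of AE, severity of AE, and the relationship to study medication will be recorded". This is the only place where a symptom is attributed to the drug or not, and nothing links that record to the withdrawal score.

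**The concern.** A withdrawal score is meant to show what happens when cannabis use falls. Here it is compared between a drug and placebo, and the protocol itself says the drug raises nausea, insomnia and abnormal dreams. Randomisation does not protect the comparison, because side effects follow from assignment. Timing may not help either: dosing runs through the whole 12-week treatment period, while participants are also trying to cut down.

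If the scale asks about any of these symptoms, two different processes feed the same total. A higher varenicline score could then be read as worse withdrawal when it is a side effect. Or a true reduction in withdrawal could be cancelled by side effects and go unseen. What is at stake is the meaning of a reported arm difference in withdrawal, or of a reported absence of one.

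**Working it through.** **Inputs from the documents.** The four relative risks (RRs) and 95% CIs under Potential Risks, the description of the scale, and the planned between-arm mixed model.

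**Not in the documents.** The 19 items, the scoring range, the SD of the score, and the placebo frequency of each symptom. The only placebo rate given is for any treatment-emergent event ("With an estimated placebo treatment-emergent AE rate of 75", in per cent), which says nothing about single symptoms.

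**Step 1: are the stated RRs consistent with their intervals?** The event counts are not given, so the RRs cannot be re-derived. Each can be checked against the geometric midpoint √(lower × upper), with SE(log RR) = ln(upper/lower)/(2 × 1.96) and z = ln(RR)/SE.

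| Symptom | RR (95% CI) | Midpoint | SE | z |
|---|---|---|---|---|
| Nausea | 3.21 (2.71–3.80) | 3.209 | 0.0862 | 13.5 |
| Insomnia | 1.50 (1.26–1.79) | 1.502 | 0.0896 | 4.5 |
| Abnormal dreams | 2.79 (2.09–3.72) | 2.788 | 0.1471 | 7.0 |
| Headache | 1.20 (1.00–1.45) | 1.204 | 0.0948 | 1.92 |

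All four agree with their intervals. The first three exclude 1. Headache does not clearly do so (two-sided p about 0.054), so the point rests on nausea, insomnia and abnormal dreams.

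**Step 2: how many extra symptoms could the drug produce?** For an assumed placebo frequency p0, equal for each symptom, the excess per varenicline participant is p0 × (RR − 1). For the three symptoms the sum is p0 × (2.21 + 0.50 + 1.79) = 4.50 × p0. Headache adds 0.20 × p0, giving 4.70 × p0.

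| Assumed p0 | Three symptoms | With headache |
|---|---|---|
| 2% | 0.09 | 0.09 |
| 5% | 0.23 | 0.24 |
| 10% | 0.45 | 0.47 |
| 15% | 0.68 | 0.71 |

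These are extra adverse-event reports per participant, not points on the withdrawal scale. They show only that the drug effect on these symptoms need not be trivial.

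**Step 3: can this be turned into a shift in the withdrawal score?** No. That would need the item list, the scoring range and the SD, and also the chance that a symptom reported at some time during treatment falls in the 24 hours before a given rating. The direction follows if items overlap: the varenicline score goes up. If no item overlaps, the shift is exactly zero.

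**Step 4: does the plan deal with it elsewhere?** The weekly adverse-event review holds the symptom type, severity and relation to the drug. The analysis sections use it for the safety comparison only. No section uses it to adjust, restrict or interpret the withdrawal score.

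**The case against.** The strongest objection is that the decisive fact lies outside the documents. Bias exists only if scale items cover the listed symptoms, and no item is named. This stands in part: the point must be put conditionally. It does not remove the point, because the sponsor holds the item list and can settle the matter quickly, and the plan is silent in either case.

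A reader might infer more than the documents support:

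- **That the scale does not ask about cause.** The one-sentence description is silent on attribution. Silence in a summary does not show what the instrument asks.
- **That the comparison is biased against varenicline.** It can be, if items overlap. It has not been shown to be.
- **That varenicline raises headache.** The interval starts at 1.00.
- **That a false-positive rate can be attached.** Taking SE = 0.5/(1.96 + 0.84) = 0.18 SD and an assumed shift of 0.1 or 0.2 SD, a two-sided 5% test would reject in about 9% or 20% of trials. But the shift is not derived from anything, and the SE comes from the power statement for cannabis use sessions, a different outcome. These figures should not be carried forward.
- **That withdrawal differences should be claimed only if a reduced score confirms them.** Nausea, sleep or dream items may also be true withdrawal symptoms. Removing them can remove real signal, so a mandatory gate could itself hide a benefit.

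It is also fair to say that withdrawal is not among the specific or exploratory aims, carries no hypothesis and drives no sample size. Recording a symptom both as an adverse event and on a scale is ordinary practice, and the adverse-event data could help a careful reader afterwards. All of this limits the importance of the point. It does not replace a rule fixed before unblinding.

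**Conclusion.** The point holds in conditional form and as a minor one. The plan compares withdrawal between arms on a symptom-severity scale, reports that the drug raises nausea, insomnia and abnormal dreams, and has no step to tell the two apart. If items overlap, a drug effect can be read as worse withdrawal or can mask a reduction.

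The conclusion rests on one assumption that the documents cannot confirm: that at least one of the 19 items covers a listed drug effect. The size of any shift cannot be estimated from the documents, and its lower bound is zero. Only an additional analysis is affected. The primary analysis of cannabis use sessions, the safety comparison and the planned enrolment ("approximately 90 participants per group for a total sample size of approximately n=180") are untouched.

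**What to change.** Add the following to Additional Data Analysis, before unblinding:

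1. List the withdrawal-scale items that match a varenicline effect named under Potential Risks: nausea, vomiting, insomnia, abnormal dreams, constipation, flatulence and headache. State in advance whether headache is counted, given its weaker evidence. If no item matches, say so, and the matter is closed.
2. Run the same mixed model on the score without the listed items, as a pre-specified sensitivity analysis.
3. Report the reduced and the full published score side by side, and interpret any arm difference in withdrawal in light of both. Do not make the reduced score a condition for reporting or claiming a difference.

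The cost is one extra model on data already collected. The drawback is that the reduced score is not the published total and may omit true withdrawal symptoms, which is why it stands beside the full score and does not replace it. Marking the items before unblinding matters most, because a choice made after seeing the results would be open to dispute.
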